Cover letter

Study protocol

ORIGINAL TITEL:

Comparison between the caudal block and other methods of postoperative pain relief in children undergoing circumcision: A prospective randomized study

Institution review board number (IRB number: 70130623).

Approval date 13\06\2023

The study conforms to the provisions of the Declaration of Helsinki in 1995 (as revised in Edinburgh 2000) and it was ethically approved by the Research Committee for Government Hospitals, Salmaniya Medical Complex, Kingdom of Bahrain (IRB number: 70130623).

Selecting the best analgesia method in pediatrics is so important. This is a randomized a prospective study conducted on 90 children who underwent circumcision. The results showed that circumcision in pediatrics using a caudal block can provide longer analgesia for the patient.

ABSTRACT

Background:

Caudal block (CB), dorsal nerve penile block (DPNB), and systemic opioids are common techniques used in pediatric surgeries to provide analgesia for penile surgery such as circumcision.

Aims: This study aimed to compare the effectiveness of the CB with other methods of postoperative pain release.

Material and Methods: The main operation pediatric theater and post-anesthesia recovery unit (PACU) in the Government Hospitals, Salmaniya Medical Complex, Bahrain.

Study subjects: Successive children aged 3 months to 3 years who had American Society of Anesthesiologists with Physical Status classification one and who had undergone elective circumcision

surgery were recruited., Children were randomized to one of three modalities of intraoperative analgesia: CB, or DPNB. And systemic opioids.

study design: Prospective, Observation-randomized, case-controlled trial study. a study Sample size: all patients, for a total of 90 boys going for circumcision surgery. I was recruited over the course of four months, starting in May 2023. The patients will be divided into three groups: A (CB), B systemic opioids, and C (DPsNB). All patients had operations and were observed, and the three groups were compared based on hemodynamic stability, pain scores, duration of sedation,

analgesia need, and parental satisfaction. where the Face, Leg, Activity, and Cry Consolability s(FLACC) pain scale and behaviors were used to observe and compare the three Groups.

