COVER LETTER

Statistical Analysis Plan

ORIGINAL TITEL:

Comparison between the caudal block and other methods of postoperative pain relief in children undergoing circumcision: A prospective randomized study

This study was approved by the research ethics committee operates Institution Review Board number 70130623

The study conforms to the provisions of the Declaration of Helsinki in 1995 (as revised in Edinburgh 2000) and it was ethically approved by the Research Committee for Government Hospitals, Salmaniya Medical Complex, Kingdom of Bahrain (IRB number: 70130623).

Data management

The collected data were recorded then presented and statistically analyzed by computer using SPSS 27.0 for Windows (*SPSS Inc., Chicago, IL, USA*) and Prism Graphpad version 9.4.1 (*Graphpad, San Diego, USA*). A test of normality was done using the Kolmogorov-Smirnov test. Kruskal-Wallis test was used to compare between groups for numerical variables, while Chi-square and Fisher's Exact test were used for categorical variables. Linear regression analysis was used to detect the predictors of pain scale. All tests were two-sided. The accepted level of significance in this work was ($p \leq 0.05$). A p -value ≤ 0.01 was considered highly statistically significant and $p > 0.05$ was considered non-statistically significant.

Results

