A total of 90 patients had participated in this current study. The study subjects were classified into 3 main groups. The first group (group A) received general anesthesia with caudal block including 29 patients. The second group (Group B) represented general anesthesia with an opioid group with a total of 33 participants, while the last group (Group C) was patients with a penile block 28 patients. Group B was significantly older in comparison with the other two groups, while Group A was the youngest age group as described in Table 1. No significant difference had been observed regarding operation duration among the three groups. Sevo Mac consumption is significantly lower in group A in comparison with the other two groups. Fentanyl consumption intra and post-operative is higher in group B followed by group C, while the lowest level of consumption with among group A patients. Participants' heart rates are shown in Figure 1. Group C significantly showed a higher mean heart rate intraoperative, 5, 10, 20, 30, and 60 minutes postoperative, while group B showed the lowest mean heart rate in the three groups ($p < 0.005$). The behavioral score is represented in figure 2 which had been measured 5, 10, 20, 30, and 60 minutes postoperative. Group C significantly demonstrated a higher percentage of severe discomfort in comparison with the other two groups in 5, 10, 20, and 30 minutes post-operative (82.1, 25.0%, 21.4%, and 3.6% respectively). The percentage of severe discomfort in group B in 5, 10, 20, and 30 minutes post-operative was 18.2, 6.1%, 3.0%, and 0.0% respectively, while only one patient expressed severe discomfort in 5, 10, and 20 minutes in group A. The pain scale was much higher among group C, while group A showed the lowest mean pain scale (Figure 3).

Table 2 represents the crying scale (5, 10, 20, 30, 60 minutes postoperative) among the studied groups. Group C showed a higher percentage of crying in comparison with the other two groups, however, the relation was non-significant.

The movement scale also was significantly different between the 3 groups in 5, 20, and 30 minutes post-operative (Table 3). Similarly, a significant difference was shown between the 3 groups in the agitation scale in 5, 10, and 30 minutes postoperative (Table 4). Table 5, demonstrated a

statistically significant difference between the 3 groups on the posture scale in 5, and 30 minutes post-operative.

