30 minutes postoperative				
Not crying	13 (44.8)	15 (45.5)	14 (50.0)	0.912
Crying but responds to tender Loving care	16 (55.2)	18 (54.5)	14 (50.0)	

60 minutes postoperative

[figure not shown]
Not crying	17 (58.6)	19 (57.6)	12 (42.9)	0.407
Crying but responds to tender Loving care	12 (41.4)	14 (42.4)	16 (57.1)	

The comparison between groups was done using Chi square test (χ^2)

[figure not shown]
5 Minutes

10 Minutes

[figure not shown]

20 Minutes

[figure not shown]

- Relaxed and comfortable
- Mild discomfort
- Moderate pain
- Severe discomfort/pain

30 Minutes

60 Minutes

Behavioral score among studied groups. *Fisher's exact test was used* FLACC scores from 0-10 , zero is analgesia, 1-3 is for mild pain, 4-6 is for moderate pain, and 7-10 is for severe pain

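### About 36 group-by-time comparisons are each judged at p ≤ 0.05 with no primary outcome, testing order or adjustment, so claims at isolated later time points are unprotected

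*SAP*

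**What the plan says.** The Protocol abstract sets the outcome domains side by side: "the three groups were compared based on hemodynamic stability, pain scores, duration of sedation", followed by analgesic need and parental satisfaction. It ranks none of them and names no principal time point.

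Under Data management, the SAP assigns tests by variable type: "Kruskal-Wallis test was used to compare between groups for numerical variables", while "Chi-square and Fisher's Exact test were used for categorical variables". It adds "All tests were two-sided" and then gives the threshold: "The accepted level of significance in this work was" p ≤ 0.05. A result at p ≤ 0.01 earns a stronger label, and p > 0.05 "was considered non-statistically significant". No model across time and no multiplicity adjustment is described for these comparisons.

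The SAP Results section then reads the scales one time at a time, for example "The movement scale also was significantly different between the 3 groups in 5, 20, and 30 minutes post-operative". Agitation is called different at 5, 10 and 30 minutes, posture at 5 and 30, severe discomfort at 5, 10, 20 and 30, and heart rate at all six times. Crying is reported as non-significant. The legend of the figure headed "Behavioral score among studied groups" gives FLACC cut-offs, so this score may be a categorised form of the pain scale.

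**The concern.** A threshold of 0.05 limits the error of one test. Here it is applied dozens of times, and each positive is stated as a finding about a particular scale at a particular minute. No familywise claim has to be written down for this to over-call, because the conclusions are drawn test by test. With no ranked outcome, a reader cannot tell which comparison was meant to carry the conclusion. If the behavioral score and the pain scale are both FLACC, one measurement also supplies two sets of tests. At stake is which of the later or isolated time-point statements can be relied on.

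**Working it through.** **1. Is testing per time and unadjusted?** SAP Table 2 gives crying counts by group (29, 33 and 28 children). An uncorrected 3×2 Pearson chi-square at each time gives p = 0.344, 0.375, 0.200, 0.912 and 0.407 at 5, 10, 20, 30 and 60 minutes. All five match the printed values, so for this scale the answer is yes.

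**2. Count of tests** (SAP, Results and tables)

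| Outcome | Documented | Inferred from the common schedule |
|---|---|---|
| Heart rate (intraoperative plus 5 times) | 6 | 0 |
| Behavioral score | 5 | 0 |
| Crying | 5 | 0 |
| Movement | 3 | 2 |
| Agitation | 3 | 2 |
| Posture | 2 | 3 |
| Pain scale | 0 | 5 |
| Total | 24 | 12 |

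This gives 24 + 12 = 36. The Table 1 tests, the pairwise comparisons and the five regressions are left out.

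**3. Error if no group differs.** The documents state no familywise rate, so there is no figure to reproduce.
- Expected false positives: 36 × 0.05 = 1.8. The expectation does not depend on correlation.
- At least one, under independence: 1 − 0.95^36 = 84.2%. With the 24 documented tests alone: 1 − 0.95^24 = 70.8%.
- Under correlation, by simulation of Kruskal-Wallis tests with group sizes 29/33/28. Correlations are assumed (between scales / between times), with heart rate independent of the other scales: 0.3/0.3 gives 79%, 0.5/0.5 gives 70%, 0.5/0.7 gives 62%, 0.7/0.7 gives 54%, 0.8/0.8 gives 44%.
- If heart rate is correlated with the rest as well (7 scales × 5 times = 35 tests), 0.7/0.7 gives about 46% and 0.8/0.8 about 35%.

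**4. Does adjustment change any reported statement?** The severe-discomfort percentages in the SAP Results convert to counts: 82.1% of 28 = 23, 18.2% of 33 = 6, and so on. Group A is one child at 5, 10 and 20 minutes, and is taken as 0 at 30 because the text mentions that child only at the earlier times. The test is an exact 3×2 test of severe versus not severe.

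| Minutes | A/29 | B/33 | C/28 | Exact p | Holm over four times |
|---|---|---|---|---|---|
| 5 | 1 | 6 | 23 | 3×10⁻¹¹ | 1×10⁻¹⁰ |
| 10 | 1 | 2 | 7 | 0.030 | 0.075 |
| 20 | 1 | 1 | 6 | 0.025 | 0.075 |
| 30 | 0 | 0 | 1 | 0.31 | 0.31 |

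Holm: 0.025 × 3 = 0.075 at 20 minutes. At 10 minutes, 0.030 × 2 = 0.060 is raised to 0.075 to keep the order. At 30 minutes there is one event. Each placement has probability 29/90, 33/90 or 28/90, and only group C's is as small as that observed, so p = 28/90 = 0.31.

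**The case against.** The strongest reply is that the no-difference scenario does not resemble these results. The SAP names 18 significant outcome-times (heart rate 6, behavioral score 4, movement 3, agitation 3, posture 2) against about 1.8 expected. A reader might infer from the familywise figure that scattered positives on movement, agitation and posture cannot be told apart from chance. The documents do not support that for the pattern: 8 of an inferred 15 such tests are positive, against 15 × 0.05 = 0.75 expected. In simulation, 8 or more has null probability of about 0.6% or less for assumed correlations up to 0.7 within a scale and 0.5 between scales. This part of the reply stands. It concerns the scales together and does not validate any one time point.

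A reader might also infer that a false positive is more likely than not. That depends on correlations the documents do not give, and it fails when correlation is high. If two of the scales are the same measure, some correlation is high. Even so, 35-45% is far above 5%.

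Twelve of the 36 tests are inferred. For the pain scale, the available text says only that group C was much higher, and the by-time statements come from regressions. The 24 documented tests alone still give 70.8% under independence.

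It would also go too far to say that movement, agitation and posture are offered as support for a particular block. The text says only that the three groups differ on them.

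Finally, the Fisher tests behind the behavioral score probably used all four categories, so their p-values may differ from those recomputed here. That is fair. The recomputation tests the contrast the sentence states, which is the percentage with severe discomfort.

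**Conclusion.** The point holds in a limited form. One unadjusted threshold governs about 36 comparisons with no ranking. If the groups did not differ, about 1.8 false positives would be expected. The chance of at least one is 84% under independence, roughly 50-80% under moderate correlation and about 35-45% under high correlation, all correlations being assumed. These figures are conditional on no difference anywhere and do not show that any reported difference is false. The 5-minute difference in severe discomfort survives any reasonable adjustment. The severe-discomfort claims at 10, 20 and 30 minutes do not survive Holm over the four times on the recomputed contrast, and the 30-minute one rests on one child. That result assumes group A had no severe case at 30 minutes and uses a severe/not-severe split.

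**What to change.** Report Holm-adjusted p-values over the time points within each scale and across scales. Within a five-time scale the first step is 0.05/5 = 0.01. Pooled over all 36 tests it is 0.05/36 = 0.0014. Label single-time results for movement, agitation, posture, crying and heart rate as exploratory. If the behavioral score is the pain scale in categories, say so and count it once, which leaves 36 − 5 = 31 tests.

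One overall test per scale over 5-60 minutes, with FLACC as the headline, would be a useful addition. It cannot be derived from the existing p-values and needs reanalysis of the patient-level data. Because the SAP already contains results, that choice must be declared post hoc; it does not restore confirmatory error control.

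The adjusted p-values and labels cost little: a few sentences and a calculation on p-values already obtained. The downside is that some borderline time-point results lose the significant label.

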Table 6 explains that the type of block, fentanyl intraoperative and postoperative was the predictor of the 5-minute pain scale, while the type of block was only the significant predictor of the 10, 20, and 30-minute pain scale. The type of block and weight of participants were the predictors of the pain scale 60 minutes postoperative

Comparison between the caudal block and other methods of postoperative pain relief in children undergoing circumcision: A prospective randomized study

This study was approved by the research ethics committee operates Institution Review Board number 70130623

Table 1. Demographic data of children who underwent circumcision

Demographic data of children who underwent circumcision Variables	Group A (n=29) Mean±SD	Group B (n=33) Mean±SD	Group C (n=28) Mean±SD	P-value*	Significant pairs**
Age (months)	16.0±7.5	41.8±43.3	16.3±19.7	0.002	Group A vs.s Group B AND Group B vs Group C
Weight (KG)	10.3±2.4	11.3±3.8	9.0±5.1		0.130
Operation duration (minutes)	14.6±3.5	15.1±4.6	16.3±6.1		0.523
Sevo mac	0.5±0.3	2.0±1.6	1.5±0.2	<0.001	Group A vs. Group B AND Group A vs. Group C
Fentanyl intraoperative	9.9±5.4	22.1±9.1	16.4±5.4	<0.001	Group A vs Group B Group A vs. Group C AND Group B vs. Group C
Fentanyl postoperative	4.8±3.1	10.5±4.6	5.2±2.5	<0.001	Group A vs. Group B AND Group B vs. Group C

Comparison between the caudal block and other methods of postoperative pain relief in children undergoing circumcision: A prospective randomized study

This study was approved by the research ethics committee operates Institution Review Board number 70130623

Table 2:

represents the crying scale (5, 10, 20, 30, 60 minutes postoperative) among the studied groups. Group C showed a higher percentage of crying in comparison with the other two groups, however, the relation was non-significant

Crying scale (5, 10, 20, 30, 60 minutes postoperative) among studied groups

Brief title: Participants' Crying Scale

[figure not shown]
Variables	Group A (n=29) N (%)	Group B (n=33) N (%)	Group C (n=28) N (%)	P -value
5 minutes postoperative				
Not crying	19 (65.5)	19 (57.6)	13 (46.4)	0.344
Crying but responds to tender Loving care	10 (34.5)	14 (42.4)	15 (53.6)	
10 minutes postoperative				
Not crying	15 (51.7)	17 (51.5)	10 (35.7)	0.375
Crying but responds to tender Loving care	14 (48.3)	16 (48.5)	18 (64.3)	
20 minutes postoperative				
Not crying	19 (65.5)	16 (48.5)	12 (42.9)	0.200
Crying but responds to tender Loving care	10 (34.5)	17 (51.5)	16 (57.1)	

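### Intraoperative fentanyl, very probably Group B's allocated treatment, is tested across arms as a result; the A-B and B-C differences are not evidence that a block reduces opioid need

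*SAP*

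**What the plan says.** The Protocol abstract (study subjects) sets out the allocation: "Children were randomized to one of three modalities of intraoperative analgesia: CB, or DPNB. And systemic opioids". The opioid is not named. Under study design, the need for analgesia is one of the listed comparisons, without saying whether this means intraoperative, postoperative or rescue use.

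The SAP Results describe the arms:
- A: "The first group (group A) received general anesthesia with caudal block including 29 patients"
- B: "The second group (Group B) represented general anesthesia with an opioid group with a total of 33 participants"
- C: "the last group (Group C) was patients with a penile block 28 patients"

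Only B's description mentions an opioid. Table 1 then gives fentanyl for all three arms, in the order A, B, C, with no unit printed:
- "Fentanyl intraoperative 9.9±5.4 22.1±9.1 16.4±5.4 <0.001", with all three pairs flagged as significant
- "Fentanyl postoperative 4.8±3.1 10.5±4.6 5.2±2.5 <0.001", with A-B and B-C flagged

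The Results text presents both rows as one finding: "Fentanyl consumption intra and post-operative is higher in group B followed by group C". The paragraph on Table 6 also names intraoperative and postoperative fentanyl, beside type of block, as predictors of the 5-minute pain scale. Neither document says how fentanyl was to be given in any arm, or separates allocated from supplementary or rescue use.

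**The concern.** A quantity that is part of the assigned treatment in one arm cannot also serve as that arm's outcome. If Group B's allocated opioid is fentanyl, a higher intraoperative amount in B is at least partly what allocation was meant to produce. A small p-value for A-B or B-C then mixes assignment with need. Because analgesia need is a listed comparison, a reader will probably take the fentanyl rows as evidence that the blocks spare opioid.

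The second issue is what was compared. The arm descriptions suggest block against opioid, but Table 1 shows intraoperative fentanyl in both block arms. Operations averaged about 15 minutes and scoring began 5 minutes after surgery, so early pain scores in A and C may carry the effect of fentanyl as well as of the block. The Protocol's opening summary credits the caudal block with longer analgesia and does not mention the fentanyl given in that arm.

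**Working it through.** **Inputs (SAP Table 1).** n: A 29, B 33, C 28. Intraoperative fentanyl, mean±SD: 9.9±5.4, 22.1±9.1, 16.4±5.4. Postoperative fentanyl: 4.8±3.1, 10.5±4.6, 5.2±2.5. Mean weight in kg: 10.3, 11.3, 9.0.

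**1. Reproducing the plan's figure.** The stated test is Kruskal-Wallis, which needs patient data. A one-way ANOVA from the summary statistics checks consistency only.
- Overall mean = (29×9.9 + 33×22.1 + 28×16.4)/90 = 16.40.
- Between-group sum of squares ≈ 2297; within-group = 28×5.4² + 32×9.1² + 27×5.4² ≈ 4254.
- F = (2297/2)/(4254/87) ≈ 23.5 on 2 and 87 df, p = 7×10⁻⁹.

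Pairwise differences (95% CI = difference ± 1.96×√(SD₁²/n₁ + SD₂²/n₂); p from Welch tests):

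| Pair | Intraoperative | Postoperative |
|---|---|---|
| B−A | 12.2 (8.5 to 15.9), p=3×10⁻⁸ | 5.7 (3.8 to 7.6), p=3×10⁻⁷ |
| C−A | 6.5 (3.7 to 9.3), p=3×10⁻⁵ | 0.4 (−1.1 to 1.9), p=0.59 |
| B−C | 5.7 (2.0 to 9.4), p=0.004; 0.011 after Bonferroni ×3 | 5.3 (3.5 to 7.1), p=6×10⁻⁷ |

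For postoperative fentanyl F = 24.8, p = 3×10⁻⁹. Table 1's p-values and flagged pairs agree with its means and SDs. The question is what they mean.

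**2. Intraoperative fentanyl in the block arms relative to B.**
- Raw means: A 9.9/22.1 = 45%; C 16.4/22.1 = 74%.
- Mean fentanyl over mean weight: A 9.9/10.3 = 0.96; B 22.1/11.3 = 1.96; C 16.4/9.0 = 1.82. As shares of B: A 49%, C 93%. A ratio of means only approximates the mean per-kg amount.

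**3. How many block-arm children received any.** If each mean covers every child in the arm, the share with a non-zero amount is at least mean²/(mean² + SD²).
- A: 98.01/(98.01 + 29.16) = 0.771; ×29 = 22.4, so at least 23 of 29.
- C: 268.96/(268.96 + 29.16) = 0.902; ×28 = 25.3, so at least 26 of 28.

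Fentanyl in these arms was therefore not confined to a few children.

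**4. How much of B's total excess is intraoperative.** Totals: A 14.7, B 32.6, C 21.6.
- B over A: 12.2 of 17.9 = 68%.
- B over C: 5.7 of 11.0 = 52%.

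The Results sentence puts both periods together, so at least half of the excess it describes arose while B's allocated modality was being given.

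**The case against.** The strongest reply is that nothing here invalidates the comparison. Several parts of it stand, and they rule out stronger readings that a reader might infer.

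- **That fentanyl is stated to be B's drug.** It is not. The documents say only systemic opioids, or an opioid. Fentanyl is the only candidate named, so the inference is strong, but the conclusion stays conditional on it.
- **That all of B's higher consumption follows from allocation.** This cannot be extended to postoperative fentanyl. There B is about twice A and C (10.5 against 4.8 and 5.2), which could be a genuine difference in need. The documents do not say whether it was scheduled or given on demand.
- **That the trial does not compare a block with an opioid.** Too strong. Block-based and opioid-based strategies can still be compared, and any supplementary fentanyl belongs to the strategy.
- **That fentanyl explains Group A's lower pain.** The direction is wrong. A had the least fentanyl and the lowest mean pain scale, so extra fentanyl cannot account for A's advantage.
- **That the result can be restated as the block's added value on top of fentanyl.** That needs similar background fentanyl across arms, which the 45% and 74% ratios contradict.

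It is also fair to say that fentanyl sits in a table headed as demographic data and that neither document explicitly argues effectiveness from it. That is only a partial answer: the row records something given after allocation, carries a p-value and flagged pairs, and is narrated as a finding.

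**Conclusion.** The point holds in a limited form. The intraoperative A-B difference (12.2) and B-C difference (5.7) at least partly reflect what Group B was allocated, and they should not be read as evidence that a block reduces opioid need. This rests on fentanyl being B's allocated opioid, which is very probable but not stated.

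That Groups A and C also received intraoperative fentanyl comes directly from Table 1 and does not depend on that inference. Its size does depend on scaling: 45% and 74% of B's mean unscaled, about 49% and 93% per kg of mean weight. What can be claimed is a comparison of strategies, not of block alone with opioid alone. The A-C intraoperative difference (6.5) is free of the allocation problem, but it shows opioid sparing only if dosing followed need, which the documents do not say. The pain results are not overturned.

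**What to change.** - Report intraoperative fentanyl by arm as treatment exposure, with its unit and per kg. Name Group B's opioid.
- Withdraw the A-B and B-C intraoperative p-values as evidence on analgesia need. Treat A-C as descriptive unless the records show need-driven dosing.
- Split the Results sentence so that postoperative fentanyl is reported separately. Present it as the analgesia-need comparison only if the records show it was given on demand.
- Word the objective and conclusion as a comparison of block-based and opioid-based strategies, with the fentanyl amounts beside them.
- Reconcile the arm descriptions in the Protocol abstract and SAP Results with Table 1, stating how fentanyl was actually given in each arm.

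The cost is mostly rewording of the abstract, Results and Table 1. No new patients or measurements are needed, but the opioid's name, the unit, the per-kg amounts and the on-demand status must be taken from existing records. The price is a narrower claim and two significant p-values no longer used as evidence.

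### Each scale is tested separately at five times in the same 90 children, so the plan yields no overall group difference with a confidence interval and no test of whether the difference changes with time

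*SAP*

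**What the plan says.** The SAP's Data management section sets out the between-group methods: "Kruskal-Wallis test was used to compare between groups for numerical variables, while Chi-square and Fisher's Exact test were used for categorical variables". It adds one model: "Linear regression analysis was used to detect the predictors of pain scale". "All tests were two-sided", and each is judged at 0.05. No mixed model, GEE, repeated-measures analysis of variance or per-child summary over time is named, and neither is a primary time point or a multiplicity adjustment.

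The Results section describes the behavioural score as one "which had been measured 5, 10, 20, 30, and 60 minutes postoperative". Table 2 gives one crying p-value for each of those times, with 29, 33 and 28 children in groups A, B and C throughout. The other scales are reported as lists of times. For example, "The movement scale also was significantly different between the 3 groups in 5, 20, and 30 minutes post-operative". Agitation is listed at 5, 10 and 30 minutes, and posture at 5 and 30. The regression of the pain scale, as described for Table 6, is also given by time: block type plus both fentanyl variables at 5 minutes, block type alone at 10, 20 and 30, and block type plus weight at 60.

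**The concern.** The aim in the Protocol abstract is to compare the effectiveness of the caudal block with that of other methods of postoperative pain relief. Five unconnected p-values per scale do not give one answer to that question.

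- **No overall estimate.** No scale has a between-group difference over the recovery hour with a confidence interval.
- **No test of change over time.** Movement is listed at 5, 20 and 30 minutes but not 10, and agitation at 5, 10 and 30 but not 20. Without a group-by-time term, the plan cannot separate a real change in the group difference from results falling either side of 0.05.
- **Repeated chances of a false positive.** Each scale gets five tests at 0.05 with no stated control.
- **Unused information.** Five ratings of one child, taken together, say more than one rating alone, by an amount that depends on how strongly they are correlated.

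**Working it through.** **1. Reproduce Table 2.** Inputs are the numbers of children crying in A, B and C out of 29, 33 and 28. The check is a Pearson chi-square on each 2×3 table with 2 degrees of freedom and no continuity correction, for which p = exp(−χ²/2).

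| Minutes | Crying A, B, C | χ² | p recomputed | p in Table 2 |
|---|---|---|---|---|
| 5 | 10, 14, 15 | 2.131 | 0.3445 | 0.344 |
| 10 | 14, 16, 18 | 1.959 | 0.3755 | 0.375 |
| 20 | 10, 17, 16 | 3.223 | 0.1995 | 0.200 |
| 30 | 16, 18, 14 | 0.184 | 0.9122 | 0.912 |
| 60 | 12, 14, 16 | 1.799 | 0.4068 | 0.407 |

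All five agree, so each time was analysed alone. Tables 3 to 5 are not in the text available for this review. For movement, agitation and posture, separate testing is therefore an inference from the lists of significant times.

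**2. False positives per scale.** If the five tests were independent, the chance of at least one false positive is 1 − 0.95⁵ = 22.6%. Simulating five correlated 2-df chi-square statistics (200,000 sets, common correlation between the underlying normal deviates) gives about 21%, 18%, 15% and 10% at correlations of 0.3, 0.5, 0.7 and 0.9.

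**3. Precision.** The documents give no within-child correlation ρ, so it is assumed and varied. With equal correlation between any two times, the variance of a child's five-time mean relative to one rating is (1 + 4ρ)/5. The effective number of observations per child is 5/(1 + 4ρ):

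- ρ = 0.3: variance ratio 0.44, 2.27 observations
- ρ = 0.5: 0.60, 1.67
- ρ = 0.7: 0.76, 1.32
- ρ = 0.9: 0.92, 1.09

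**4. Crying pooled over time.**

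- A: (10+14+10+16+12)/(5×29) = 62/145 = 42.8%
- B: (14+16+17+18+14)/(5×33) = 79/165 = 47.9%
- C: (15+18+16+14+16)/(5×28) = 79/140 = 56.4%

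The three-group chi-square is 5.433. Dividing it by 1 + 4ρ gives p = 0.066 at ρ = 0, 0.29 at 0.3, 0.40 at 0.5, 0.49 at 0.7 and 0.58 at 1.

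**5. Does the group difference look constant?** The Results give severe discomfort in C as 82.1%, 25.0%, 21.4% and 3.6% at 5, 10, 20 and 30 minutes. In B it is 18.2%, 6.1%, 3.0% and 0.0%. The C minus B gap is therefore 63.9, 18.9, 18.4 and 3.6 points. Reading the text as one child in A at each of the first three times (1/29 = 3.4%) and none at 30 minutes, C minus A is 78.7, 21.6, 18.0 and 3.6 points. The gap shrinks sharply after 5 minutes.

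**6. Weights in an area under the 5–60 minute curve.** By the trapezoid rule, the scores at 5, 10, 20, 30 and 60 minutes get weights 2.5, 7.5, 10, 20 and 15, out of 55. The 5-minute score gets 2.5/55 = 4.5%, and the last two together get 35/55 = 64%.

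**The case against.** The best defence is that nothing here is invalid. Each test uses one value per child, so there is no double counting within a test. A reader might infer that repeated ratings of the same children make the reported p-values wrong. They do not, and this part of the defence stands.

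A reader might also infer that pooling would reveal a crying effect. Taking A against C alone, the pooled p-value is about 0.02 if ratings of the same child are uncorrelated and about 0.05 at a correlation of 0.1. But A and C are the widest of three pairs, and near-zero correlation between ratings minutes apart is hard to defend. At 0.3 the A-C p-value is already 0.12, and the three-group test that matches Table 2 is non-significant at every correlation.

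The uneven pattern is also limited. Block type is reported as a predictor of pain at all five times, the behavioural score differs at four consecutive times, heart rate differs throughout, and crying differs at none. Only movement, agitation and posture are uneven. Whether their gaps are near misses or clear nulls cannot be judged without their tables, so the documents do not support calling them noise.

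Finally, an average over time could hide the 5-minute signal. Later scores may also reflect postoperative fentanyl, which differs between groups in Table 1 (4.8, 10.5 and 5.2). The first point is right and shapes the fix. The second also stands: a repeated-measures model does not resolve it.

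**Conclusion.** The concern holds as one of efficiency and interpretability. The plan and results treat five ratings per child as five unrelated comparisons, so they give no overall difference with an interval and no group-by-time test. The chance of a false positive per scale is at most 22.6%, if the tests are independent, and about 18% at a between-time correlation of 0.5.

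The evidence is direct for crying and inferred for movement, agitation and posture. The precision gain assumes equal correlation between times and is not known. It is substantial at 0.3, where the information per child slightly more than doubles, and slight at 0.9. For crying, the only scale with visible counts, the conclusion would not change. The change is worth making, but the existing tests need not be withdrawn.

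**What to change.** For each scale, fit one model over all five times with group, time and group-by-time: a mixed or ordinal mixed model for the pain and behaviour scores, and GEE logistic regression with robust standard errors for crying. Test group and group-by-time jointly first. With three groups and five times this has 2 + 2×4 = 10 degrees of freedom. Then report the A-B and A-C differences with 95% confidence intervals, both overall and at each time, because the severe-discomfort gap is far from constant.

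Do not use the area under the 5–60 minute curve as the main summary. It would give least weight to the time at which the reported separation is greatest.

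Results already stand in the SAP, so label the new analysis post hoc. One model per scale reduces five tests to one for that scale. It does not settle which scale is primary, and multiplicity across scales remains a separate matter.

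The cost is SAP wording, a modest amount of analysis on data already collected, and a working assumption about within-child correlation, which robust standard errors largely cover in the GEE.
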